Atrial fibrillation (AF) is the most common arrhythmia seen in clinical practice, accounting for one-third of rhythm-related hospitalizations. The prevalence of AF in the United States is 1% overall and more than 10% in people over age 80 years, with approximately 70% of cases in patients between 65 and 85 years of age. As Americans age, the number of patients with AF is expected to increase 150% by 2050, with more than 50% of patients being octogenarians or older. The increasing burden of AF is expected to lead to a higher incidence of stroke, as patients with AF have a five to seven fold greater risk of stroke than the general population. Patients with a stroke in AF patients is 4 to 5% per year. Patients with a stroke due to AF have worse prognoses than patients with stroke without AF. All Oral anticoagulants (OACs) are an important therapy for patients with AF as they decrease the rate of stroke by more than two-thirds.

The clinical benefit of warfarin is only seen in patients who consistently maintain their international normalized ratio (INR) values within the therapeutic range (2.0-3.0). ¹⁶ The median times in the therapeutic range in the ARISTOTLE¹⁷, ROCKET AF¹⁸, RE-LY¹⁹, and ENGAGE²⁰ trials were 62%, 55%, 64%, and 68%, respectively. As part of quality improvement efforts, there is significant interest in measuring and improving performance of physicians in prescribing anticoagulation for patients with AF. The CHADS₂ and CHA₂DS₂-VASC scores have been developed to support providers in identifying patients with AF who are at an increased risk for stroke. ^{21,22} Paradoxically, anticoagulation use is no higher, or declines, as the risk of stroke, as measured by these scores, increases. ²³ This is in large part due to the fact that physicians and patients are concerned about the risk of bleeding in higher-risk populations, and they may underappreciate the net benefit from anticoagulants, including stroke prevention. In any case, approximately 40-60% of patients with AF at risk of stroke are not prescribed anticoagulation therapy. ^{15,24-30} This translates to over 50,000 preventable strokes each year in the United States with a number needed to treat of approximately 25 patients to prevent 1 stroke.

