The delayed intervention cohort will receive usual care over the initial study period. After the date on which at least 80% of eligible study participants have at least 12 months of follow-up time, "fresh" pharmacy claims data for the delayed intervention cohort that was generated and locked at the time of randomization will be used to assess trial eligibility, and those patients without evidence of an OAC medication fill during the 12 months prior to randomization will be included in the primary and secondary analyses as the delayed intervention arm. Patients randomized to the delayed intervention arm with evidence of an OAC medication fill during the 12 months prior to randomization will be excluded from the trial and will not be included in analyses. The baseline characteristics of the delayed intervention patients will be examined at the same time point as the early intervention patients, meaning at the time of randomization. The primary outcome is a comparison of the proportion of patients not on OAC during the 12 months prior to randomization, who were started on OAC over the course of the follow-up through the date on which at least 80% of eligible study participants have at least 12 months of follow-up time in the early versus the delayed intervention arm. A total of approximately 80,000 patients (randomized 1:1) across all participating Data Partners (Aetna, Harvard Pilgrim, HealthCore, Humana, and Optum) will be enrolled from participating Data Partners across the United States. Similar to the early intervention cohort, the patients in the delayed intervention cohort will be assigned to wave 1 or wave 2 ("pseudo" wave assignments) depending on the difficulty in identifying the patient's provider (the intent is to handle them the same way as was done for the early intervention arm). The follow-up for the delayed intervention patients will start on the date the wave 1 or 2 mailings take place for a given Data Partner's early intervention cohort. The follow-up time for the primary outcome will be 12 months from the date at which at least 80% of eligible study participates are enrolled (date on which early intervention materials are mailed).

[figure not shown]

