An electronic program, developed by the central coordinating center (Harvard Pilgrim), will be used by the participating Data Partners to identify their eligible member-patients who meet the inclusion and exclusion criteria for this trial. The patient billing claims records will not be linked to pharmacy data until after randomization, so the inclusion criterion of no OAC medication fill during the 12 months prior to randomization will not be applied until after randomization. This will be done immediately for the early intervention group, and in the delayed intervention group, not until 12 months after at least 80% of early intervention mailing have occurred. Patients will be randomly assigned in a 1:1 ratio, via the program, to early patient-level and provider-level intervention versus delayed provider-level intervention. A list of eligible member-patients will stay at each Data Partner, and identifiable patient-level data will not be shared with the central coordinating center (Harvard Pilgrim) or the statistical analysis center (Duke Clinical Research Institute). The Data Partners will remove any individuals who cannot be included in research studies, which includes certain Centers for Medicare and Medicaid Services and Administrative Services Only patients. There are several other reasons that could prevent mailing of the intervention, to members and/or their providers (list may not be exhaustive):

- Member is now deceased
- Member disenrolls from health plan
- Member transitions to a plan that does not allow for inclusion in research
- Member has a recent anticoagulant dispensing
- Member has an incorrect/missing/bad address
- Member is added to a do-not-contact list at the health plan

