6. Patients with recent P2Y12 antagonist use (i.e., clopidogrel, prasugrel, or ticagrelor within 90 days of prior to randomization)

F. STUDY DESIGN AND DURATION

As described in detail in the protocol, the study is a prospective, randomized, and open-label educational intervention trial. Patients with AF and a CHA₂DS₂-VASc score of 2 or greater were randomized in a 1:1 ratio to an early intervention cohort and a delayed intervention cohort within each participating health plan. The definition for OAC medication fill was an OAC medication dispensing or at least 4 INR tests in the claims data.³ The claims records of the patients randomized to the early intervention cohort were then linked to “fresh” (i.e., about 1 month old) pharmacy claims data at the time of randomization. Patients without evidence of an OAC medication fill during the 12 months prior to randomization were included in the patient-level and provider-level early educational intervention (patients randomized to this early intervention with evidence of an OAC medication fill during the 12 months prior to randomization were excluded from the trial). In addition to usual care, these patients and their providers received a one-time mailing at trial start. There were two waves of mailing for the early intervention cohort at most sites due to the practical challenges of claims data: the patients were assigned to wave 1 if they had a provider easily identified in the data (i.e., the provider associated with the most recent AF diagnosis is indeed an individual provider), and they were assigned to wave 2 if it was difficult to identify a provider (e.g., the first identified provider is actually a facility). Follow-up time started on the date of the respective wave 1 and wave 2 mailings for the early intervention patients.

The delayed intervention cohort will have received usual care over the initial study period. After the date on which at least 80% of all eligible study participants have at least 12 months of follow-up time, the treatment status of the delayed intervention group will be assessed via the Sentinel data available at that time, in addition to “fresh” pharmacy claims data. The providers of patients in the delayed cohort who did not receive OAC medication during the course of follow-up and still meet all inclusion criteria will receive the provider-only education intervention (patients will not receive the educational materials unless no provider can be identified for a mailing).

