1. 33% OAC initiation rate in the delayed intervention arm
2. 38% OAC initiation rate in the early intervention arm (5% absolute improvement in OAC initiation over the 33% OAC initiation expected in the delayed intervention arm over 1-year follow-up)
3. 1-year attrition rate: 30% dropout or lost-to-follow-up
4. Two-sided type I error rate of 0.05
5. Roughly 10,000 patients who meet the inclusion/exclusion criteria will yield more than 99% power to detect a 5% absolute difference

Power	Total sample size (2-arm)	Early Intervention	Delayed Intervention
90%	5610	2805	2805
95%	6910	3455	3455
99%	9718	4859	4859

2. Important Secondary Outcome of Stroke or TIA

A study with approximately 80,000 patients could provide reasonable power for stroke or TIA outcome under certain assumptions listed below:

- 1-year stroke or TIA rate: 18% among patients not treated with OAC
- 1-year stroke or TIA rate: 7% among patients treated with at least 1 OAC fill
- Duration of follow-up: 1 year
- 33% of delayed intervention patients will have at least 1 fill of OAC, meaning the 1-year stroke or TIA rate in the delayed intervention group would be 14.4%
- 1-year attrition rate: 30% dropout or lost-to-follow-up
- Two-sided type I error of 0.05
- If 38% of early intervention patients have at least 1 fill of OAC (meaning the 1-year stroke or TIA rate in the early intervention group would be 13.82%, i.e., an absolute reduction of 0.55%), the study will have 46% power to detect this 0.55% reduction. However, if 40.5% of early intervention patients have at least 1 fill of OAC (meaning the 1-year stroke or TIA rate in the

early intervention group would be 13.54%, i.e., an absolute reduction of 0.83%), the study will have 80% power to detect this 0.83% reduction.

8. The sample size has 80% power to detect a 0.5% absolute reduction in stroke, assuming a cumulative 1-year incidence of stroke of 4.2% in control (delayed intervention arm) patients and 3.7% in intervention (early intervention arm) patients. The assumption is that patients not on oral anticoagulation have an annual stroke rate of 5%, and stroke will be reduced by 50% (HR=0.5) in the treated (anticoagulated) population. The 80% power requires that 52% of early intervention arm patients are treated at 1-year as compared to 33% in the control arm.

II. STATISTICAL ANALYSIS

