All primary analyses will be based on modified intention-to-treat (mITT) principle (i.e., all identified early intervention patients who met eligibility and were mailed the intervention will be included; using “pseudo” wave assignments, all identified delayed intervention patients who met eligibility at the time of corresponding early mailings will be included). Since the additional exclusions after randomization will be applied in the same way, using the same time points for both the early and delayed intervention groups, we expect there will be no effect from these additional exclusions on the randomization. The mITT analysis will include the following:

- Early intervention members who were mailed a letter, with follow-up beginning on the date of mailing (up to two dates per site and the dates varied by site).
- Delayed intervention members who were not on treatment at the date of mailing (wave assignments were made for the delayed as described earlier in section I.F) with follow-up beginning on that date.

An as-randomized analysis will be performed for an incident occurrence of the primary endpoint as a sensitivity analysis (using a washout of 365 days). Randomization occurred prior to treatment status assessment per the study design. Therefore, the as-randomized analysis will include people who were on treatment as well as others who were not truly eligible for the study (e.g., had incomplete or invalid addresses or had a “do not contact” status).

Potential sensitivity analysis for mITT analysis: There may be differential loss to follow up between the early and delayed intervention groups because some members did not have valid mailing addresses, though we did not assess the addresses of the members in the delayed intervention arm at the time of early intervention mailings. It is not possible to retrospectively ascertain the address status of the delayed intervention group as of the date on which mailing would have occurred for that group. We can estimate the magnitude by referring to the early intervention group, and in the early intervention group, we can compare the baseline characteristics and experience of the individuals who had no valid address to those who do.

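### The stroke/TIA and stroke power figures treat 80,000 as the eligible number, although the protocol calls 80,000 the number randomized, before OAC users and others are removed

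*SAP*

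**What the plan says.** The power paragraph for the important secondary outcome appears in the protocol synopsis, protocol XIV.A.2 and SAP I.G.2. The SAP version opens: "A study with approximately 80,000 patients could provide reasonable power for stroke or TIA outcome under certain assumptions listed below". Protocol XIV.A.2 goes further and calls the trial well powered for this outcome. The assumptions are 18% and 7% one-year stroke/TIA rates without and with OAC, 33% uptake in the delayed arm, "1-year attrition rate: 30% dropout or lost-to-follow-up" and "Two-sided type I error of 0.05". The stated powers are 46% (38% early-arm uptake) and 80% (40.5% uptake). For stroke alone, 80% is stated at 52% uptake.

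On what the 80,000 are, protocol VI says "A total of approximately 80,000 patients (randomized 1:1) across all participating Data Partners" will be enrolled. On the order of events, protocol IX says "the inclusion criterion of no OAC medication fill during the 12 months prior to randomization will not be applied until after randomization". Protocol VI then takes patients with a prior-year fill out of the trial and out of the analyses. SAP I.F also removes those who die, disenroll or start OAC between randomization and mailing. SAP II restricts the early arm of the mITT set to patients who were mailed, and says that, by contrast, "the as-randomized analysis will include people who were on treatment as well as others who were not truly eligible for the study".

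**The concern.** The only deduction named in the power paragraph is for dropout or loss to follow-up. Follow-up starts at mailing, so that allowance cannot cover patients who leave between randomization and mailing. If 80,000 is the randomized count, the mITT set on which these outcomes are analysed is smaller than the one the power refers to.

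At stake is how a null result for stroke/TIA or stroke would be read. It would be set against powers, and a well-powered label, that the analysed set may not have.

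**Working it through.** **Inputs (SAP I.G.2).**
- Stroke/TIA, delayed arm: 0.33 × 7% + 0.67 × 18% = 14.37%.
- Stroke/TIA, early arm: 13.82% at 38% uptake; 0.405 × 7% + 0.595 × 18% = 13.545% at 40.5% uptake.
- Stroke, delayed arm: 0.67 × 5% + 0.33 × 2.5% = 4.175% (stated as 4.2%). Early arm: 0.48 × 5% + 0.52 × 2.5% = 3.70%.
- 1:1 allocation, two-sided 0.05, 30% attrition.

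**Formula.** With n per arm and p̄ the mean of the two rates,

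power = Φ( [ |p0 − p1| − 1.96·√(2p̄(1−p̄)/n) ] / √(p0(1−p0)/n + p1(1−p1)/n) ).

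**Step 1: reproduce the stated figures.** n = 80,000 × 0.70 / 2 = 28,000.
- 14.37% v 13.82%: (0.00550 − 1.96 × 0.002941) / 0.002941 = −0.090, power 46.4% (stated 46%).
- 14.37% v 13.545%: (0.00825 − 1.96 × 0.002929) / 0.002929 = 0.857, power 80.4% (stated 80%).
- 4.175% v 3.70%: (0.00475 − 1.96 × 0.001644) / 0.001644 = 0.930, power 82.4% (stated 80%).

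At 40,000 per arm, with no attrition, the results would be 60.8%, 92.0% and 93.2%, which do not match. So the calculation starts from 80,000 eligible patients, deducts 30%, and deducts nothing else.

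**Step 2: deduct removals before follow-up.** The removal fraction r is an assumption; the documents give none for this cohort. n = 28,000 × (1 − r).

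| Removed | n per arm | Stroke/TIA, 38% uptake | Stroke/TIA, 40.5% uptake | Stroke, 52% uptake |
|---|---|---|---|---|
| 0% | 28,000 | 46% | 80% | 82% |
| 10% | 25,200 | 43% | 76% | 78% |
| 20% | 22,400 | 39% | 71% | 73% |
| 40% | 16,800 | 31% | 59% | 61% |
| 60% | 11,200 | 22% | 43% | 45% |

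**Step 3: credit person-time before censoring.** The plan's calculation treats the 30% lost as giving no information, but the planned Cox and log-rank analyses use their time up to censoring. Take event hazard λ = −ln(1 − p), censoring hazard η = −ln(0.70) and one year of follow-up. The probability of an observed event is λ/(λ+η) × (1 − e^−(λ+η)). With D total events, power = Φ(½√D·|ln HR| − 1.96).
- 80,000 eligible: 54%, 87% and 89%.
- Number eligible that still gives the stated 46% and 80% for stroke/TIA: about 65,400, so removal of (80,000 − 65,400)/80,000 ≈ 18% is absorbed. For stroke at 80% it is about 62,400, or 22%.
- 40% removed: 36%, 67% and 69%. 60% removed: 25%, 50% and 52%.

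**Step 4: primary endpoint.** The documents' table asks for 9,718 patients in total for 99% power on 33% v 38%. Even with 60% removed and 30% attrition, 80,000 × 0.40 × 0.70 = 22,400 remain.

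**The case against.** The strongest reply is that 80,000 may already be the count after the OAC check. The sentence in protocol VI says the 80,000 will be enrolled. The synopsis dates enrollment at the early mailing, which follows the early-arm check, and OAC users are described as excluded from the trial. SAP I.G.1 also states its primary-endpoint number in patients who meet the eligibility criteria. On that reading the stated powers stand, and this cannot be ruled out. It is not the more natural reading, though. The same sentence labels the 80,000 as randomized. Protocol XIV.A allows enrolled patients to be ineligible at mailing. The delayed arm has the same enrollment date although its OAC check is run about 12 months later. The stroke/TIA paragraph carries no eligibility qualifier.

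A second reply is that the planned time-to-event analysis is more efficient than the power method. This is right, and step 3 gives the credit. Follow-up beyond 12 months would add more: at an assumed 15-month average, about 30% removal is absorbed. The power paragraph itself assumes one year.

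A third is that the plan already concedes 46% at its own planning uptake and makes each 80% conditional on higher uptake. That tempers the consequence, but each conditional figure still needs the right denominator.

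Two stronger readings are tempting and should be resisted. A reader might infer that power was computed as if all 80,000 were analysable; step 1 shows that the 30% attrition was taken off. A reader might also take the protocol's background figures as the removal fraction: the Introduction's "approximately 40-60% of patients with AF at risk of stroke are not prescribed anticoagulation therapy", or the Study Rationale's 52% with a fill. The first is general background, and the second is any fill over 2006 to 2015 at three Data Partners. Neither measures fills in the prior 12 months in this cohort.

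**Conclusion.** The concern holds conditionally. The three secondary powers rest on 80,000 eligible patients less 30% attrition, while protocol VI calls the 80,000 randomized and several groups are removed between randomization and the start of mITT follow-up. If 80,000 is the randomized count, the plan's own method overstates power: by about 3 to 4 points for each figure at an assumed 10% removal, and by about 16, 22 and 21 points (from the recomputed 46%, 80% and 82%) at 40%. With person-time credited over one year, up to about 18% removal leaves the stated values intact; at 40% or 60% they are still too high. The actual fraction is not in the documents, so no single corrected power can be given here. The primary endpoint keeps ample power throughout.

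**What to change.** In the synopsis, protocol XIV.A.2 and SAP I.G.2, label 80,000 as randomized before the OAC exclusion. Restate the three powers on the expected mITT number, with the attrition assumption shown, and revise the well-powered and reasonable-power wording to match.

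For the mITT number, use the early-arm mailed count, which should be available because the SAP describes the early mailings as done, plus a separate delayed-arm count. Doubling the early count is only approximate: SAP II says delayed-arm addresses were not assessed at the early mailings, so bad-address patients leave one arm only.

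If 80,000 was meant as the post-exclusion number, correct the wording in protocol VI and state the larger randomized number instead.

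The cost is one power calculation and some rewording. No extra patients are needed. If 80,000 is the randomized count, the restated power will probably look less favourable.

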 - In a Sentinel feasibility assessment of identified health plan members meeting similar inclusion and exclusion criteria as this trial, 33% had evidence of OAC initiation in a 1 year period of follow-up.
- 38% OAC initiation rate in the early intervention arm (a 5% absolute improvement in OAC initiation over the 33% OA initiation expected in the delayed intervention arm over 1-year follow-up)
- 1-year attrition rate: 30% dropout or lost-to-follow-up
- Two-sided type I error of 0.05
- Roughly 10,000 patients (Table below) will yield more than 99% power to detect a 5% absolute difference

[figure not shown]

Power	Total sample size (2-arm)	Early Intervention	Delayed Intervention
90%	5610	2805	2805
95%	6910	3455	3455
99%	9718	4859	4859

Total Number of Patients in a 2-arm study (Unadjusted for dropouts)

OAC Initiation Endpoint (33% Control Rate), continuity corrected Chi-square

2. Important Secondary Analysis of Stroke or TIA

A study with approximately 80,000 patients is well powered for the outcome of stroke or TIA over the course of the follow-up through the date on which at least 80% of eligible study participants have at least 12 months of follow-up time, under certain assumptions listed below:

- 1-year stroke or TIA rate: 18% among patients not treated with OAC
- 1-year stroke or TIA rate: 7% among patients treated with at least 1 OAC fill
- Duration of follow-up: 1 year
- 33% of delayed intervention patients will have at least 1 fill of OAC, meaning the 1 year stroke or TIA rate in the delayed intervention group would be 14.4%
- If 38% of early intervention patients have at least 1 fill of OAC (meaning the 1 year stroke or TIA rate in the early intervention group would be 13.82%, i.e., an absolute reduction of 0.55%), the study will have 46% power to detect this 0.55% reduction. However, if 40.5% of early intervention patients have at least 1 fill of OAC (meaning the 1 year stroke or TIA rate in the early intervention group would be 13.54%, i.e., an absolute reduction of 0.83%), the study will have 80% power to detect this 0.83% reduction.

- 1-year attrition rate: 30% dropout or lost-to-follow-up
- Two-sided type I error of 0.05

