- The sample size has 80% power to detect a 0.5% absolute reduction in stroke, assuming a cumulative 1-year incidence of stroke of 4.2% in control (delayed intervention arm) patients and 3.7% in intervention (early intervention arm) patients. The assumption is that patients not on oral anticoagulation have an annual stroke rate of 5%, and stroke will be reduced by 50% (HR=0.5) in the treated (anticoagulated) population. The 80% power requires that 52% of early intervention arm patients are treated at 1-year as compared to 33% in the control arm.

B. POPULATIONS FOR ANALYSIS

All analyses will be based on a modified intention-to-treat principle (i.e., all identified early intervention patients who meet eligibility and are mailed the intervention will be included; using "pseudo" wave assignments, all identified delayed intervention patients who meet eligibility at the time of corresponding early mailings will be included in the analysis). The primary endpoint will be calculated based on the proportion of patients with evidence of at least one OAC prescription fill over the course of the follow-up through the date on which at least 80% of eligible study participants have at least 12 months of follow-up time. An as-randomized analysis will be performed for the primary endpoint as a sensitivity analysis. All possible person-time will be used to assess participants' outcomes; patients will have different duration of follow-up and that will be accounted for in the analyses. Patients will be censored from the analysis at the time of death, disenrollment from the health plan, loss of medical or pharmacy coverage, or change in eligibility for inclusion in research based on health plan membership. The statistical analysis plan (SAP) provided more information and outlines in detail how granular aggregate data will be received from each Data Partner in lieu of patient-level data.

XV. OUTCOME DEFINITIONS

All outcome definitions will be based on available claims data.

- 1. Evidence of OAC start: the proportion of AF patients who have at least 4 INR values measured or who fill at least one OAC prescription for apixaban, dabigatran, edoxaban, rivaroxaban, or warfarin over the course of the follow-up through the date on which at least 80% of eligible study participants have at least 12 months of follow-up time

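### The 80% power for stroke credits everyone treated by one year with a full year of protection, although all patients enter untreated; the stroke/TIA figures share the problem unless their 7% input already assumes early starts

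*SAP*

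**What the plan says.** The stroke claim is in SAP I.G.2 and is repeated in Protocol XIV.A.2 and the synopsis. The untreated rate is 5% per year, "stroke will be reduced by 50% (HR=0.5) in the treated (anticoagulated) population", and the sample size is said to give 80% power for 4.2% v 3.7%. The condition attached is "The 80% power requires that 52% of early intervention arm patients are treated at 1-year as compared to 33% in the control arm".

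For stroke/TIA the untreated 1-year rate is 18%, and the other input is "1-year stroke or TIA rate: 7% among patients treated with at least 1 OAC fill". With 33% of the delayed arm filling, power is stated as 46% at 38% early-arm uptake and 80% at 40.5%.

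The 33% comes from a feasibility assessment in which "33% had evidence of OAC initiation in a 1 year period of follow-up" (Protocol XIV.A.1). Patients with a fill in the 12 months before randomization are excluded (SAP I.E). Those who start between randomization and mailing are excluded in both arms, and follow-up begins at mailing or the matching pseudo-wave date (SAP I.F and II).

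**The concern.** The arm-level rates are mixtures weighted by treatment status at the end of the year. The 33% and 52% are shares who have started by month 12; nobody is on treatment at time zero. A hazard ratio can act only after the drug is started, so a patient who starts in month 9 has about 3 months of reduced hazard, not 12. Neither document assumes a start-time distribution or a persistence rate, although the SAP analyses time to first OAC fill and tabulates the primary endpoint at 42, 90 and 183 days (Table 2b).

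If the between-arm event difference is smaller than planned at a given uptake, the uptake said to give 80% power does not give it. A null clinical result would then be read against a sensitivity the trial may not have had. Stroke/TIA is labelled important in both documents, and Protocol XIV.A.2 calls the study well powered for it.

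**Working it through.** **Inputs (SAP I.G.2 and I.F).** About 80,000 patients, allocated 1:1. "1-year attrition rate: 30% dropout or lost-to-follow-up", so 80,000 x 0.7 / 2 = 28,000 per arm. "Two-sided type I error of 0.05". Duration 1 year. Power = Φ(|p1 − p2| / SE − 1.96), with SE² = [p1(1 − p1) + p2(1 − p2)] / 28,000.

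**1. The plan's own figures.**
- Stroke, delayed arm: 0.67 x 5% + 0.33 x 2.5% = 4.175%. Early arm: 0.48 x 5% + 0.52 x 2.5% = 3.70%. SE = 0.00164, so 0.00475 / 0.00164 − 1.96 = 0.93 and power is 82.4% (stated 80%). Putting HR 0.5 on the hazard gives 4.19% v 3.72% and 81.3%.
- Stroke/TIA: 0.67 x 18% + 0.33 x 7% = 14.37%. At 38%: 0.62 x 18% + 0.38 x 7% = 13.82%, power 46.4% (stated 46%). At 40.5%: 0.595 x 18% + 0.405 x 7% = 13.545%, power 80.4% (stated 80%).

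No start time enters any of these.

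**2. Stroke with the hazard changing at OAC start.** Untreated hazard h0 = −ln(0.95) = 0.0513; treated h1 = 0.5 x h0. A patient who starts at time s (in years) has 1-year risk 1 − exp(−[h0·s + h1·(1 − s)]).

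Assumptions, none of them in the documents: hazards are constant, nobody stops, the 33% background starts are uniform over the year in both arms, and the extra 19 points (52 − 33) in the early arm are uniform over a window w.

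The mean risk of a background starter is 3.77%, so the delayed arm is 0.67 x 5% + 0.33 x 3.77% = 4.59%. The arm difference is 0.19 x (5% − mean risk of an extra starter).

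| Window w for extra starts | Mean risk, extra starter | Early arm | Difference | Power at 52% |
|---|---|---|---|---|
| 42 days | 2.68% | 4.15% | 0.44% | 72% |
| 3 months | 2.84% | 4.19% | 0.41% | 66% |
| 6 months | 3.15% | 4.24% | 0.35% | 52% |
| 12 months | 3.77% | 4.36% | 0.23% | 27% |

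Uptake needed for 80% power becomes about 55%, 59% and 72% for the 3-, 6- and 12-month windows.

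**3. What pushes power up.** The plan's 28,000 discards dropouts altogether, but the analysis keeps their time to censoring. If the 30% attrition is exponential, mean follow-up in the year is (1 − 0.7) / −ln(0.7) = 0.84 years, or about 34,000 person-years per arm from 40,000. With 34,000 per arm the four stroke figures become about 80%, 74%, 60% and 31%. Follow-up beyond 12 months also helps: with 28,000 per arm and a 3-month window, stroke power is about 78% at 15 months and 87% at 18. With all starts uniform over 12 months, 80,000 patients, exponential attrition and 18 months, it is 56%. The runs beyond 12 months ignore stopping and the delayed provider mailing.

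**4. Stroke/TIA under two readings of the 7%.**
- *On-treatment rate.* The same model with h0 = −ln(0.82) and h1 = −ln(0.93) gives, for 3-, 6- and 12-month windows at 28,000 per arm, about 34%, 26% and 14% at 38% uptake and 64%, 50% and 26% at 40.5%.
- *Ever-filler rate.* The mixture in step 1 is then plain total probability and credits nobody with day-0 treatment. But 7% is hard to reach with spread-out starts. If starts are uniform, events before the first fill alone average 1 − 0.18 / −ln(0.82) = 1 − 0.907 = 9.3%, above 7% even with perfect protection afterwards. With a common start time and perfect protection, that time could be no later than ln(0.93) / ln(0.82) = 0.366 years, about 4.4 months.

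**The case against.** A reader might infer that all three figures are upper bounds that the design cannot reach. The documents do not support that. The stated power drops 30% of patients entirely and stops at 12 months, whereas the SAP uses all person-time and expects more than 12 months for most patients. Full-year credit with attrition treated as censoring gives 53.7%, 87.1% and 87.8%, above the stated 46%, 80% and 80%. The plan's simplifications therefore pull in both directions.

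Nor is a shortfall of fixed size established. It depends on start times that the documents do not give. The intervention is a one-time mailing, so extra starts may well come early; spreading them evenly over 12 months is the unfavourable end of the range. With extra starts within 42 days and partial person-time counted, stroke power is about 80%.

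The stroke/TIA figures are also less exposed. Their 7% is worded as a rate among patients with at least one fill, so it may already average over time before the first fill and time off drug. No source is given, and the documents cannot settle it. Step 4 shows only that this reading carries its own unstated assumption of early starts.

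Finally, these are secondary outcomes, and the SAP is guarded: "A study with approximately 80,000 patients could provide reasonable power for stroke or TIA outcome under certain assumptions listed below". It discloses 46% power at the planned 38% uptake and says that stroke needs 52%. A careful reader already knows that clinical power is weak at expected uptake.

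All of this stands and limits the scope. It does not remove the point for stroke, where 5%, HR 0.5 and a share treated at 1 year yield the stated power only with treatment from day 0.

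**Conclusion.** The stroke power of 80% rests on an exposure assumption that the design contradicts. On the plan's own terms it falls to between about 72% and 27% as the extra starts spread from 42 days to 12 months, given uniform background starts, constant hazards and no stopping. Partial person-time and longer follow-up bring it back to about 80% or more only if the extra starts come soon after mailing or follow-up is long. Stopping would lower it, and the Protocol Introduction itself cites average non-adherence of 50% in chronic disease.

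For stroke/TIA the point is conditional: the same problem if the 7% is on-treatment, an undisclosed early-start assumption if it is an ever-filler rate. Either way the documents need to say which. This is an unstated timing and persistence assumption, not a slip of arithmetic, since the plan's sums reproduce.

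**What to change.** In SAP I.G.2, Protocol XIV.A.2 and the synopsis:

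- Recompute arm-level incidence with the untreated hazard before OAC start and the treated hazard after it, using the start-time distribution from the feasibility cohort and a stated persistence assumption.
- State whether the 7% is an on-treatment or an ever-filler rate, and give its source.
- Replace the single power figures, and the well-powered wording in Protocol XIV.A.2, with the restated power or the uptake needed for 80%, over a range of start timing and follow-up length. Say how dropouts' partial follow-up is counted.

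The cost is recalculation and wording. The stated power is likely to become less favourable. Primary-endpoint power, sample size and trial conduct do not change.
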